# **Telephone Calls**

Research staff will contact study participants by phone 24-72 hours after receiving each vaccine dose throughout the study, including pre-transplant vaccines, post-transplant vaccines, and Additional Study Visit(s). Research staff will ask the participant about potential side effects of the immunization. If the participant reports adverse symptoms there will be a follow-up call on day  $7 \pm 2$  days to assess resolution. Participants will also be contacted 5-7 days before each study visit to confirm the appointment. Contact can be made using site standard procedures and/or mechanisms (i.e. automated or manual phone call, text message, or email) .

The following information with be collected during the telephone calls:

- Concomitant medication review
- Adverse events. Participants will be asked if they have experienced any of the following symptoms to assess adverse events:
  - o Pain, swelling, redness, or itching at the vaccine injection site
  - Headache
  - o Fever
  - o Nausea
  - Signs of a severe allergic reaction: hives, a fast heartbeat, dizziness, weakness, difficulty breathing, or swelling of the face and throat
- Additional symptoms experienced by participants will be recorded to assess adverse events

## 7.3.4 Transplant Surgery

For participants who receive only one vaccine dose prior to transplant, a blood sample (28 ml) will be obtained for antibody titers before/at transplant surgery. All other participants (who received two or more vaccines prior to transplant) will have no research activity on the day of transplant surgery.

#### 7.4 Evaluation at Completion of Study Intervention

## 6 Month Post-Transplant Visit

This study visit will occur 6 months ( $\pm$  2 weeks) after the participant's kidney transplant procedure. The following procedures will be performed during this visit:

- 1) Review of medical and surgical history, and medications, and laboratory test results
- 2) Symptom assessment and ECOG performance status
- 3) Physical exam including vital signs and measurement of weight
- 4) Blood draw A 28 mL blood specimen will be collected from each participant.
- 5) Self-collection of cervical/vaginal and oral samples for HPV DNA detection.
- 6) Self-collection of urine for HPV DNA detection from participants who consent to collection of optional urine samples.
- 7) Collection of eyebrow hairs (collected by research staff) for future viral DNA testing from participants who consent to collection of optional samples for biobanking for future studies
- 8) Self-collection of male genital samples for future HPV DNA testing from participants who consent to collection of these optional samples for biobanking for future studies
- 9) Interviewer-administered follow-up questionnaire to obtain information about changes in exposures and behaviors between study visits (Appendix F)

10) Review of inclusion/exclusion criteria and study requirements

# 12 Month Post-Transplant Visit

This study visit will occur 12 months ( $\pm$  2 weeks) after the participant's kidney transplant procedure. The following procedures will be performed during this visit:

- 1) Review of medical and surgical history, medications, and laboratory test results
- 2) Symptom assessment and ECOG performance status
- 3) Physical exam including vital signs and measurement of weight
- 4) Pregnancy test (urine or blood) for women who meet both of the following criteria:
  - a. Received only one or two vaccines earlier in the study, AND
  - b. Are able to become pregnant (women who have had both ovaries removed or a tubal ligation will not be required to have a pregnancy test)

Women who are pregnant will not receive the Gardasil® 9 HPV vaccine.

- 5) Participants who have received two vaccine doses prior to transplant will receive the third dose of the vaccine. Participants who have received only one dose of the vaccine prior to transplant will receive the second dose of the vaccine at this visit.
- 6) Blood draw A 28 mL blood specimen will be collected from each participant.
- 7) Self-collection of cervical/vaginal and oral samples for HPV DNA detection.
- 8) Self-collection of urine for HPV DNA detection from participants who consent to collection of optional urine samples.
- 9) Self-collection of male genital samples for future HPV DNA testing from participants who consent to collection of these optional samples for biobanking for future studies
- 10) Collection of eyebrow hairs (collected by research staff) for future viral DNA testing from participants who consent to collection of optional samples for biobanking for future studies
- 11) Interviewer-administered follow-up questionnaire to obtain information about changes in exposures and behaviors between study visits (Appendix F)
- 12) Review of inclusion/exclusion criteria and study requirements

#### 7.5 Post-intervention Follow-up Period

## 13 Month Post-Transplant Visit

If the participant received a vaccine dose at the 12 Month Post-Transplant Visit, the participant will return for a 13 Month Post-Transplant Visit. This visit will occur 1 month (+2 weeks) after the 12 Month Post-Transplant Visit. The following procedures will be performed during this visit:

1) Blood draw – A 10 mL blood specimen will be collected from each participant to measure HPV vaccine-type-specific antibody titers.

## 7.6 Additional Study Visit(s)

Additional Study Visits will be offered only for the purpose of completing the vaccine series for participants who are unable to receive their second or third vaccine doses in accordance to the proposed schedule of events. These Visits will be offered in the following scenarios:

- 1. Participants who only received one dose prior to transplant, and their second dose administered at 12 Month Post-Transplant Visit. These participants will receive their third dose at an Additional Study Visit 3 months (+4 weeks) after the 12 Month Post-Transplant Visit.
- 2. Participants who received two vaccine doses prior to transplant, but their transplant surgery is postponed/rescheduled/cancelled and eventually not scheduled within 12 months of the study enrollment date, will complete their three dose vaccine series at an Additional Study Visit at 12 months (±2 weeks) after Pre-Transplant Vaccine Visit 1. These participants will be considered off-study after the Additional Study Visit is completed, and follow-up calls were made, as

- discussed in Section 8.4.
- 3. Participants who receive one vaccine dose prior to transplant, but their transplant surgery does not occur within 12 months of Pre-Transplant Vaccine Visit 1, will be offered two Additional Study Visits to complete the three dose vaccine series. Additional Study Visit 1 will occur 12 months (±2 weeks) after the Pre-Transplant Vaccine Visit 1. Additional Study Visit 2 will occur 3 months (+4 weeks) after Additional Study Visit 2. These participants will be considered offstudy after the Additional Study Visits are completed, and follow-up phone calls were made, as discussed in Section 8.4.

The following procedures will be performed during the Additional Study Visits:

1) The second or third dose of Gardasil® 9 is administered.

#### 7.7 Methods for Clinical Procedures

Administration of Vaccine. The CDC HPV VIS (http://www.immunize.org/vis/hpv.pdf) will be provided to the participant prior to administration of the vaccine. The vaccine will be administered as a 0.5 mL injection in the deltoid region of the upper arm or in the higher anterolateral area of the thigh. Participants will be monitored for adverse reactions to the vaccine for 30 minutes.

**Blood specimen**. A 28 mL blood specimen will be collected from each participant at the Pre-Transplant Vaccine Visits 1, 2, and 3, at the 6 Month and 12 Month Post-Transplant Visits, and (for participants who do not complete Pre-Transplant Vaccine Visit 2) before/at transplant surgery for measurement of the primary and secondary endpoints for the study. Ten mL of blood will be collected at the 13 Month Post-Transplant Visit to measure the anamnestic response to the booster vaccine dose by assessing HPV vaccine-type-specific titers. The primary biomarker of interest, HPV vaccine-type-specific seroconversion rates, will be measured in peripheral blood that will be drawn by routine venipuncture at the time of mandated blood draws, thus there will be no added risk to the participant.

Collection of cervical/vaginal and oral samples for HPV DNA testing. Cervical/vaginal and oral samples will be self-collected at the Pre-Transplant Vaccine Visits 1, 2, and 3, and at the 6 Month and 12 Month Post-Transplant Visits for HPV DNA testing. Cervical/vaginal samples will be self-collected using the Evalyn Brush® (Rovers Medical Devices B.V., Oss, Netherlands) for female participants only. Oral samples will be self-collected using a mouthwash gargle.

Collection of urine samples for HPV DNA testing. Urine samples will be self-collected at the Pre-Transplant Vaccine Visits 1, 2, and 3, and at the 6 Month and 12 Month Post-Transplant Visits from participants who consent to the collection of optional urine samples. Approximately 20-30 mL of urine will be self-collected at each visit in a sterile urine specimen container. Urine samples will be used for HPV DNA testing.

Collection of eyebrow hair samples for future viral DNA testing. Eyebrow hair samples will be collected at the Pre-Transplant Vaccine Visits 1, 2, and 3, and at the 6 Month and 12 Month Post-Transplant Visits from participants who consent to collection of optional samples for biobanking for future studies. Clinical research staff will collect six eyebrow hairs with the attached follicle from each consenting participant using sterile tweezers. Eyebrow hair samples will be used for future viral DNA testing.

Collection of male genital samples for HPV DNA testing. Male genital samples will be collected using a validated male genital sampler collection protocol [40,46] from participants who consent to the collection of these optional samples for an exploratory analysis of detection of HPV DNA during the course of the study. This analysis is exploratory since there is no FDA-approved HPV sampling or testing protocol in males. Male genital samples will be self-collected by rubbing a dry swab over the entire exterior surface of the penis and placed into a vial. Male genital samples will be self-collected at the Pre-

Transplant Vaccine Visits 1, 2, and 3, and at the 6 Month and 12 Month Post-Transplant Visits and will be used for HPV DNA testing.

## 8. CRITERIA FOR EVALUATION AND ENDPOINT DEFINITION

# 8.1 Primary Endpoint

HPV vaccine-type-specific seroconversion rates at 12-months post-transplantation among 18-49 year old kidney transplant recipients who receive  $\geq 1$  doses of the Gardasil® 9 HPV vaccine  $\geq 30$  days prior to transplantation.

## 8.2 Secondary and Exploratory Endpoints

# Secondary Endpoint

HPV vaccine-type-specific seroconversion rates at 6- and 12-months post-transplantation stratified by number of doses (1, 2, or 3) of the vaccine given pre-transplant.

## **Exploratory Endpoints**

- 1) HPV vaccine-type-specific seroconversion rates at 12-months post-transplantation stratified by:
  - a) time elapsed between last vaccine dose and the transplant procedure;
  - b) variations in doses and types of post-transplant immunosuppressant medications; and interactions with type of transplant surgery (living donor/deceased donor);
  - c) differences in Human Leukocyte Antigen (HLA) histocompatibility between donor and recipient;
  - d) differences in biological sex (i.e. male vs. female) of the transplant recipient.
- 2) Stability of HPV vaccine-type-specific geometric mean titers (GMT) at 6- and 12-months post-transplantation and rise in HPV vaccine-type-specific GMT at the 13-month post-transplant visit.
- 3) Vaccine safety profile and allograft rejection/opportunistic infections stratified by number of vaccine doses and time between the last vaccine dose and the transplant procedure.
- 4) HPV detection in samples from the cervix/vagina, and oral cavity at baseline (pre-vaccination) and at 6- and 12-months post-vaccination, overall and by number of vaccine doses (1, 2, or 3), sexual behavior, type-specific seroconversion rates, and time elapsed between the last vaccine dose and the transplant procedure.

## 8.3 Off-Agent Criteria

Participants may stop taking study agent for the following reasons: completed the protocol-prescribed intervention, AE or serious adverse event (SAE), inadequate agent supply, noncompliance, or medical contraindications. Participants will continue to be followed, if possible, for safety reasons (e.g., telephone contact 24-72 hours after receiving each vaccine dose to ask about potential side effects of the immunization; and a follow-up call on day  $7 \pm 2$  days to assess resolution if the participant reports adverse symptoms). Participants who receive one or two doses of the vaccine in the pre-transplant period and go off-agent due to any reason stated above will be offered the post-transplant study visits at 6-months, 12-months and 13-months to collect endpoint data according to the schedule of events, even though the clinical and/or logistical situation that led to the participant going 'off-agent' might not permit giving the remaining vaccine doses at any of these visits.

# 8.4 Off-Study Criteria

Participants may go 'off-study' for the following reasons: the protocol intervention and any protocol-

required follow-up period is completed, AE/SAE, lost to follow-up, non-compliance, medical contraindications, withdraw consent, death, determination of ineligibility (including screen failure), or pregnancy. Participants whose planned transplant surgery does not occur within 12 months of enrollment will be taken 'off-study' after Additional Study Visit(s) and follow-up phone calls (described in Section 7.5.2) are completed, to finish the remaining vaccine doses of the series. All participants who do not receive transplant surgery within 12 months of enrollment will be notified prior to going off study.

# 8.5 Study Termination

NCI, DCP as the clinical study protocol sponsor has the right to discontinue the study at any time.

## 9. CORRELATIVE/SPECIAL STUDIES

## 9.1 Rationale for Methodology Selection

9.1.1 Vaccine-induced seroconversion: Serum samples obtained at baseline and at follow-up study visits will be assessed for antibodies to HPV VLP types 6/11/16/18/31/33/45/52/58 by competitive Luminex immunoassay (HPV-9 cLIA Version 2.0). For the primary endpoint, a participant will be defined as seroconverted i.e., anti-HPV 6, 11, 16, 18, 31, 33, 45, 52, or 58 positive by Merck's proprietary competitive Luminex Immunoassay (cLIA) assay if the anti-HPV serum level at the 12-months posttransplant visit is  $\ge 30, \ge 16, \ge 20, \ge 24, \ge 10, \ge 8, \ge 8, \text{ or } \ge 8 \text{ milli Merck units (mMU)/mL, respectively}$ by the cLIA assay [21,23]. The cLIA assay uses a multiplex format with each of the nine virus like particle (VLP)-types in the vaccine fixed to Luminex microspheres with distinct fluorescent properties. Antibody titers are determined in a competitive format, where type-specific phycoerythrin (PE)-labeled, neutralizing monoclonal antibodies (mAbs-PE) compete with an individual's vaccine-induced antibodies in the serum for binding to conformationally-sensitive, neutralizing epitopes on the VLPs [23,24]. There is no specific (minimum) number of serotypes required for classifying someone as seroconverted, since the seroconversion for each vaccine-serotype will be assessed independently. Further, since the cLIA antibody titers to each HPV type are determined using type-specific monoclonal antibodies, it is not possible to make a direct comparison of assay results across HPV types. Given the age of the participants, there is high likelihood of having prior sexual exposure to some, if not all, individual HPV types targeted by the nonavalent HPV vaccine. However, anti-HPV antibodies induced due to such 'natural' infection are usually detected at a much lower titer levels than the aforementioned cutoffs defined for vaccineinduced seropositivity. Type-specific sensitivity analyses, restricted to participants who are seronegative for individual types at baseline, will also be conducted. Assays will be performed at Merck Research Laboratories. If access to cLIA is not feasible due to technical or operational reasons, a 9-valent multiplex HPV assay (based on same principle/framework as the cLIA assay) developed at the NCI Frederick National Laboratory for Cancer Research (FNLCR) will be used for the study.

9.1.2 HPV detection and genotyping: HPV DNA will be extracted from cervical/vaginal (in women), oral, and, optionally, urine samples (in both genders) and male genital samples (in men) by use of commercial reagents (Qiagen, Valencia, CA). A 450 bp region of the L1 HPV genome will be amplified using the PGMY09/11 primer system, a nondegenerate, pooled primer system modified from the original, degenerate MY09/11 primer system [25]. GH20 and PC04 primers will be used to coamplify a 268 bp region of the human  $\beta$ -globin gene as an internal control for sample sufficiency. Specimens positive for the 450- and 268-bp bands of HPV and  $\beta$ -globin, respectively, will be considered positive. Specimens found negative for  $\beta$ -globin on co-amplification will be re-amplified in a single amplification reaction. Those remaining negative for  $\beta$ -globin will be excluded from analysis. HPV DNA-positive specimens will be genotyped using a reverse line-blot detection method for 37 different HPV types [26], including high-risk [oncogenic] types 16, 18, 31, 33, 35, 39, 45, 51, 52, 56, 58, 59, and 68; possible high-risk types 26, 34, 53, 66, 70, 73, and 82; low-risk [nononcogenic] types 6, 11, 40, 42, 44, 54, 61, 72, 81, and 89; and undetermined-risk types 62, 67, 71, 83, and 84 [27]. HPV-positive specimens that subsequently have negative results in the genotyping assay will be considered to be unclassified HPV-positive specimens.

Urine samples are optional because patients on dialysis may be unable to provide a urine sample. Male genital samples are optional because, unlike female cervical/vaginal HPV testing, there is limited evidence on the ideal methods for HPV testing and the clinical correlates of HPV test positivity results in men.

9.1.3 Eyebrow hair samples for future viral DNA testing. Solid organ transplant recipients are at high risk (30-fold) for non-melanoma skin cancers, most notably squamous cell skin cancer. UV exposure is a major risk factor for these cancers in immunosuppressed and immunocompetent populations. Infections have been hypothesized to play a role in the development of these malignancies, namely genus beta HPVs [28,29]. Studies of skin biopsies indicate that levels of cutaneous HPVs are higher in squamous cell cancers than normal appearing skin, and even higher among those who are immunosuppressed with cancer [30]. Eyebrow hair follicles represent a sun-exposed reservoir for HPV [31]. Compared to the general population, HPV DNA levels in these follicles are higher in those who develop squamous cell skin cancer [32], and even higher in solid organ transplant recipients [31]. There is also growing interest regarding the role of polyomaviruses in squamous cell skin cancer development [33]. Polyomaviruses reside in eyebrow hair follicles [34], and there is recent evidence that polyomavirus DNA in eyebrow hair follicles are associated with squamous cell cancer [35]. Eyebrow hair samples will be collected by research staff at the baseline and follow-up study visits from participants who consent to collection of optional samples for biobanking for future studies. Eyebrow hair samples will be stored for future viral DNA testing.

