Given the strong biological rationale, a recently convened International Agency for Research on Cancer/National Cancer Institute workshop has recommended seroconversion, and specifically immunological non-inferiority, as sufficient for a presumption of efficacy for the HPV vaccine in immunobridging studies focused on the expansion of vaccine indications [14]. Thus, the endpoint for this trial is seroconversion, and we will define efficacy as greater than or equal to 90% of the study population achieving seroconversion. The definition for positivity, or seroconversion, will be based on results of the HPV-9 cLIA (Merck) or, alternatively, a validated 9-valent HPV multiplex assay developed at the NCI Frederick National Laboratory for Cancer Research (FNLCR), which measures HPV type-specific antibodies to neutralizing epitopes on VLPs from a patient's serum sample. Seropositivity is not part of the eligibility criteria for enrollment.

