## \*Notes:

- i) Living and Deceased Donor Transplant Recipients: The study was originally restricted to participants who were expecting to receive only living donor renal transplants. However, less than a third of kidney transplants in the United States occur with kidneys from living donors. A majority of transplants are in the setting of donation of kidneys from deceased donors. To permit efficiencies in accrual, the study is amended (from version 3.5) to also open enrollment to recipients of deceased donor kidneys.
- ii) Transplant recipients of both genders: The study was originally designed to be conducted only

among women. However, in October 2018, the FDA approved an age expansion indication for the Gardasil 9 HPV vaccine for both women and men up to 45 years (from the originally approved upper age limit of 26 years), thus opening a new clinical cancer preventative option for middle-age adults of both genders [38]. The primary endpoint for the study is HPV-vaccine-type-specific seroconversion rates, which are not expected to be differential by gender, based on extrapolating from the uniformly high (>99%) seroconversion rates observed regardless of gender in studies among immunocompetent individuals. However, HPV vaccine-type-specific titer levels (GMT) differences by gender will be analyzed as a secondary endpoint, given variability in immune response titer levels observed between males and females in immunocompetent individuals (related to the differences in body mass index or hitherto unproven factors related to hormone-immune interactions [20,21]). Another advantage of expanding this study to males will be to facilitate efficiencies in accrual, since men constitute the majority (55%-65%) of all kidney transplant recipients in the United States. Although a majority of current HPV-associated cancers among solid organ transplant recipients occur among women, [2] there is increasing evidence of the link between HPV infection and oropharyngeal cancers that disproportionately affect men [39]. HPV-related oropharyngeal cancers are now the most common HPV-related cancers in the United States, surpassing even the incidence of cervical cancer. [39] The expansion of enrollment to men will also allow this study to look at the effect of HPV vaccination on persistence of oral HPV infection as a secondary/exploratory endpoint in the context of transplantrelated immunosuppression.

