# 13.4 Primary Objective, Endpoint(s), Analysis Plan

The primary objective is to estimate HPV vaccine-type-specific seroconversion rates at 12-months post-transplantation among kidney transplant recipients who receive  $\geq 1$  doses of the Gardasil® 9 HPV vaccine prior to transplantation,

An estimate of the seroconversion rate will be provided along with exact Clopper-Pearson 95% confidence intervals (CIs).

Originally (until version 3.10), the study was designed with the expectation of at least n=64 evaluable participants for the primary analysis, and the analytic plan was focused on comparisons with prespecified benchmarks (e.g., 0.75 and 0.90) of the expected seroconversion rate estimate.

In version 3.11, responding to the lower accrual expectations of between n=24 to n=28 evaluable participants in the study, the study's focus was revised to only focus on description of the estimation of the seroconversion rate and the upper limit of its one sided 95% confidence interval, as opposed to any pre-specified comparisons.

Even without pre-specified comparison benchmarks, the revised analysis plan will permit cross-study comparisons with other relevant HPV vaccination studies (e.g., those conducted among individuals undergoing solid organ transplants or other immunosuppressed individuals). The study will generate key preliminary data for testing clinically relevant hypotheses in future larger studies to evaluate the full extent of protection afforded by HPV vaccination administered prior to transplant.

With the study expecting to yield between n=24 to n=28 evaluable participants, Table 3 (below) provides expected upper limits of the one sided 95% CI for the estimates of the seroconversion rates ranging between 0.65 to 0.90.

Table 3. Expected upper limits of one sided 95% CI for seroconversion rates				
Expected accrual n=24 evaluable	Expected accrual n=28 evaluable			
participants	participants			

	One-sided 95%CI		One-sided 95%CI
Estimate P	Upper Limit	Estimate P	Upper Limit
0.65	0.8088	0.65	0.7977
0.70	0.8480	0.70	0.8380
0.75	0.8851	0.75	0.8763
0.80	0.9197	0.80	0.9123
0.90	0.9776	0.90	0.9739

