# 13.5 Secondary and Exploratory Objectives, Endpoints, Analysis Plans

#### Secondary Endpoint:

Descriptive statistics, such as probabilities and exact 95% confidence intervals, will be used to summarize HPV vaccine-type-specific seroconversion rates at 6- and 12-months post-transplantation stratified by number of doses (1, 2, or 3) of the vaccine given pre-transplant. Seroconversion probabilities will be compared between dose groups using Fisher's exact test. Armitage trend test will be used to examine whether there is a trend for increased seropositivity across dose groups. Due to the limited sample size, these tests will be sufficiently powered to detect only very large differences and will be considered exploratory.

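### Does scoring seroconversion from the 12-month titre alone, with no baseline condition, call for a change to the primary analysis?

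*Combined protocol and SAP*

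**What the plan says.** Section 9.1.1 gives the rule: "For the primary endpoint, a participant will be defined as seroconverted" for a type if the titre at the 12-month post-transplant visit is at or above that type's cut-off on the competitive Luminex assay. Each type is judged separately. The rule contains no baseline term.

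The same section then deals with prior exposure. It accepts that many participants will have met some of the vaccine types, and says that antibody from natural infection is "usually detected at a much lower titer levels than the aforementioned cutoffs". It adds: "Type-specific sensitivity analyses, restricted to participants who are seronegative for individual types at baseline, will also be conducted". Baseline and follow-up sera go through the same assay.

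Section 2.3 equates the two terms: "The definition for positivity, or seroconversion, will be based on results of the HPV-9 cLIA". It also says that serostatus plays no part in eligibility.

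Section 13.4 gives the analysis: "An estimate of the seroconversion rate will be provided along with exact Clopper-Pearson 95% confidence intervals". It mentions neither baseline serostatus nor the baseline-negative analysis. For the dose comparison, Section 13.5 compares seroconversion probabilities and then says: "Armitage trend test will be used to examine whether there is a trend for increased seropositivity across dose groups". Since version 3.11 there is no benchmark test, and Section 13.4 says that "the revised analysis plan will permit cross-study comparisons with other relevant HPV vaccination studies".

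**The concern.** In ordinary use, seroconversion means a change from negative to positive. The objective in Section 1 asks whether the vaccine provokes a response and whether that response lasts. In a single-arm trial the participant's own baseline is the main evidence on the first part. A rate that counts people positive before dose 1 shows how many are positive at 12 months. It does not show that the vaccine made them so.

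Three features make this look more serious. The safeguard, the baseline-negative analysis, sits in the laboratory section and is not repeated in Section 13. The limit that defines seronegative is not written down. And the rate is now meant for comparison with other studies, while the notes to Section 4.1.1 cite "uniformly high (>99%) seroconversion rates observed regardless of gender in studies among immunocompetent individuals" without saying whether those participants were negative at baseline. At stake would be an overstated induction claim, or a comparison of unlike quantities.

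**Working it through.** **The plan's own figures.** Table 3 is the only precision statement. Its entries are one-sided exact upper limits, U = Beta quantile at 0.95 with parameters (x + 1, n − x), where x = np is left unrounded. For n = 24 and p = 0.75, x = 18 and U = 0.8851, as printed. For n = 28 and p = 0.90, x = 25.2 and U = 0.9739, as printed. All ten entries reproduce within 0.0001. Baseline serostatus is not an input, so the table stands whichever label is used.

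**Size of the gap.** Let b be the share at or above a cut-off at baseline, k the probability that they are still so at 12 months, and s the rate in baseline negatives.

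- All-participant rate = bk + (1 − b)s
- Gap from the baseline-negative rate = b(k − s)

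The documents give none of b, k or s, so every value below is an assumption.

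| b | k | s | Gap b(k − s) | Participants of 28 |
|---|---|---|---|---|
| 0 | any | any | 0 | 0 |
| 0.10 | 1.0 | 0.90 | 0.10 × 0.10 = 0.010 | 0.28 |
| 0.10 | 1.0 | 0.65 | 0.10 × 0.35 = 0.035 | 0.98 |
| 0.20 | 1.0 | 0.75 | 0.20 × 0.25 = 0.050 | 1.40 |
| 0.30 | 1.0 | 0.60 | 0.30 × 0.40 = 0.120 | 3.36 |
| 0.30 | 0.8 | 0.90 | 0.30 × (−0.10) = −0.030 | −0.84 |

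The 12-point row needs s = 0.60, below the lowest rate in Table 3 (0.65). It also needs b = 30%, which sits poorly with the statement in Section 9.1.1 that natural titres usually fall well below the cut-offs. A 5-point gap with k = 1 needs b = 0.05/(1 − s): 20% at s = 0.75 and 50% at s = 0.90.

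**Against the precision available.** At p = 0.65 the two-sided exact 95% interval is 0.430 to 0.831 for n = 24 (width 0.401) and 0.448 to 0.819 for n = 28 (width 0.372). A 3.5-point gap is less than a tenth of either width.

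**Count examples.** With 5 of 24 positive at baseline and all still positive, 13/19 = 0.684 (exact 95% CI 0.434 to 0.874) becomes (13 + 5)/24 = 18/24 = 0.750 (0.533 to 0.902). With 4 of 5 still positive, 17/19 = 0.895 becomes 21/24 = 0.875, so the sign reverses. Each estimate lies well inside the other's interval.

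**What the plan as written delivers.** Section 9.1.1 requires the rate in all participants and, type by type, the rate in baseline seronegatives. It states cut-offs for positivity on an assay that is also run on the baseline serum. The natural reading of seronegative is below that same cut-off. Both rates in the examples above would therefore be produced without any amendment.

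**The case for a change.** The strongest case for a change is this. The baseline-negative commitment is one sentence in a methods section, with no stated interval, no stated limit and no place in Sections 13.4 or 13.5. Section 10.2.1 plans batch serology at the end of the study, so with 24 to 28 participants a limit chosen late could move several people between groups. The claim that natural titres are low is qualified by *usually* and has no figure behind it. Section 9.1.1 gives cut-offs only for the Merck assay, not for the fallback assay. A reader who sees only the published rate may take the word seroconversion at face value.

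The textual facts stand: Section 13 does not list the analysis, and the limit is implied rather than written. The rest carries less weight. This is a combined protocol and SAP, so a firm commitment in Section 9.1.1 binds as much as one in 13.4. A fallback assay would need its own positivity cut-offs for the primary endpoint anyway, and the same values would then define seronegative. A mismatch with outside studies is not shown: the figure above 99% is used to justify enrolling men, and the comparators named in Section 13.4 are studies in transplant and other immunosuppressed people, whose definitions the documents do not give.

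The obvious remedies bring problems of their own. Calling the estimate seropositivity in Sections 9.1.1, 13.4 and 13.5 would put it at odds with Sections 1.1 to 1.3, 8.1 and 8.2, which all say seroconversion. Resting every claim of induction on the baseline-negative rate would make a sensitivity analysis decisive, with about 19 to 22 people per type at b = 20%. It would also disregard a titre rise in someone already positive, which is evidence of induction too.

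**Conclusion.** No change to the plan. The primary rate is seropositivity at 12 months under another name, but the protocol says so, explains why baseline positives should be few, and already promises the analysis that separates the two quantities. The remaining gap is a cross-reference and a cut-off that analysts will fill sensibly. No test, decision rule, denominator or Table 3 entry depends on it, and an amendment under Section 14.3 would gain nothing that following Section 9.1.1 does not already give.

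The difference between the two rates is at most 3.5 points, under one participant in 28, if no more than 10% are at or above a cut-off at baseline and the baseline-negative rate is 0.65 to 0.90. It is zero if nobody is positive at baseline, and negative if baseline positives retain their status less often than negatives gain it. Over the wider assumed range (b 5 to 30%, k 0.8 to 1, s 0.60 to 0.90) it runs from −3 to +12 points. The documents do not fix b, k or s. The conclusion rests mainly on the baseline-negative analysis being carried out and reported as Section 9.1.1 promises.
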